8.2.2 Packaging

AXS-05 and bupropion SR tablets will be supplied and bottled by

and labeled at **sector and the study**. The study drug will be packaged in 50 cc bottles and labeled to blind the Investigator, the study clinic personnel, and subjects.

8.3 Study Drug Administration

All subjects will receive either AXS-05 or bupropion SR according to the kit number assigned by a randomization scheme. Eligible subjects will be assigned a unique kit that contains 4 bottles of study drug. Bottles from the assigned kits should be dispensed to the subject per the pharmacy manual and/or subject dosing instructions provided. The kit must remain on-site at all times and only the appropriate number of bottles should be dispensed to the subject at each study visit.

Designated staff at each site will dispense study drug bottles. Subjects will be instructed to take the study drug per the Treatment Period part of Section 6.1. Subjects should be instructed to return bottle(s) and any unused study drug at each study visit in order to record compliance. All study drug will be supplied and administered in a double-blind manner throughout the entire duration of the study.

8.4 Dispensing and Storage

The study drug is to be used exclusively in this clinical study according to the instructions of this protocol. The Investigator is responsible for dispensing the study drug according to the dosage scheme and for ensuring its proper storage. The Investigator or designee must confirm the receipt of study drug with a signature. A copy of this receipt must be kept by the Investigator and another copy will be stored at Axsome and/or its designee.

All study drug must be stored in an appropriate secure area (e.g., a locked cabinet in a locked room) at controlled room temperature (with a permitted range of 15°C-30°C or 59°F-86°F) and must be protected from heat and moisture. Any excursions below or above this temperature range should be communicated to Axsome Therapeutics, Inc., or its designee as soon as possible. The key to the storage area is to be kept by the Investigator or designee responsible for the study drug. The storage area will be accessible only to those persons authorized by the Investigator.

The key to the storage area is to be kept by the Investigator or designee responsible for the study drug. The storage area will be accessible only to those persons authorized by the Investigator.

8.5 Method of Assigning Subjects to Treatment Groups

Subjects who meet study entry criteria will be randomly assigned in a 1:1 ratio to AXS-05 or bupropion SR, respectively. The randomization schedule will be computer generated using a permuted block algorithm that will randomly allocate study drug to randomization numbers. The randomization numbers will be assigned sequentially. Study center will not be a blocking factor in the randomization schedule.

The randomization schedule will be prepared before the start of the study. No one involved in the study performance will have access to the randomization schedule before official unblinding of treatment assignment. No subject will be randomized into this study more than once.

8.6 Blinding and Unblinding Treatment Assignment

All subjects, Investigators, and study personnel involved in the conduct of the study, including data management, will be blinded to treatment assignment with the exception of a specified independent unblinded statistician, and clinical supply manager who will have access to the randomization code. The unblinded study personnel will not otherwise participate in study procedures or data analysis before unblinding of the study data to all study related personnel. Sponsor personnel involved in the management and monitoring of the study will be blinded to the treatment assignment.

Study personnel will strive to safeguard the integrity of the study blind to minimize bias in the conduct of the study. Treatment unblinding is discouraged if knowledge of the treatment assignment will not materially change the planned management of a medical emergency. Unblinding will be permitted in a medical emergency that requires immediate knowledge of the subject's treatment assignment. Unblinding should be discussed in advance with the medical monitor if possible. For emergency unblinding, the site will access the randomization code. If the Investigator is not able to discuss treatment unblinding in advance, then he or she must notify the medical monitor as soon as possible about the unblinding incident without revealing the subject's treatment assignment. To unblind the treatment group, the Investigator will open the envelope in which the randomization code was received. The Investigator or designee must record the date and reason for study drug discontinuation on the appropriate CRF for that subject. In all nonemergency cases, the Investigator must discuss the event with the medical monitor before unblinding the subject's treatment assignment.

If treatment assignment is unblinded for an individual subject, study personnel will be notified of that subject's treatment assignment without unblinding those of the remaining subjects in the study. Thus, the overall study blind will not be compromised. If a subject's treatment assignment is unblinded, he or she may or may not be asked to withdraw from the study. The Investigator will make this decision after consultation with the medical monitor.

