9.3.1.4 Clinical Global Impression – Severity (CGI-S)

The CGI-S scale [12] is a clinician-rated scale used to rate the severity of the subject's current state of mental illness compared with a subject population with MDD. The subject is rated on a scale from 1 to 7, with 1 indicating a "normal state" and 7 indicating "among the most extremely ill subjects." The CGI-S will be administered by the Investigator or a Sub-Investigator with extensive professional training and experience in assessing mental illness.

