9.3.3.3.3 Other Safety Assessments

9.3.3.3.3.1 Columbia Suicide Severity Rating Scale (C-SSRS)

The C-SSRS [14] is a clinician-rated instrument that reports the severity of both suicidal ideation and behavior. Suicidal ideation is classified on a 5-item scale: 1 (wish to be dead), 2 (nonspecific active suicidal thoughts), 3 (active suicidal ideation with any methods [not plan] without intent to act), 4 (active suicidal ideation with some intent to act, without specific plan), and 5 (active suicidal ideation with specific plan and intent). The C-SSRS also captures information about the intensity of ideation, specifically the frequency, duration, controllability, deterrents, and reasons for the most severe types of ideation. Suicidal behavior is classified on a 5-item scale: 0 (no suicidal behavior), 1 (preparatory acts or behavior), 2 (aborted attempt), 3 (interrupted attempt), and 4 (actual attempt). More than 1 classification can be selected provided they represent separate episodes. For actual attempts only, the actual or potential lethality is classified for the initial, most lethal, and most recent attempts.

The C-SSRS will be completed at Visits 1, 2, and 4 - 9. At Visit 1 (Screening) the C-SSRS will be completed for the subject's lifetime history of suicidal ideation and behavior, along with a recent recall period. At all other visits the C-SSRS will be completed for ideation and behavior with a recall period since the last visit.

The C-SSRS will be administered by the Investigator.

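### Protocol 8.6 orders that study personnel be told an unblinded subject's treatment, with no need-to-know limit, and no rule covers ratings made afterwards

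*Protocol*

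**What the plan says.** Protocol 8.6 opens with a general rule: "All subjects, Investigators, and study personnel involved in the conduct of the study, including data management, will be blinded to treatment assignment". It excepts an independent unblinded statistician and the clinical supply manager. A separate sentence covers the sponsor: "Sponsor personnel involved in the management and monitoring of the study will be blinded to the treatment assignment".

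In an emergency, the Investigator opens the envelope that holds the code. If there was no chance to speak to the medical monitor beforehand, "he or she must notify the medical monitor as soon as possible about the unblinding incident without revealing the subject's treatment assignment".

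The next paragraph deals with any subject who has been individually unblinded: "study personnel will be notified of that subject's treatment assignment without unblinding those of the remaining subjects in the study". It concludes that the overall blind is intact. On whether the subject stays, it says that "he or she may or may not be asked to withdraw from the study"; the Investigator decides after consulting the medical monitor.

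The following sections bear on who rates such a subject and how the data are used:

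- Protocol 7.3 encourages subjects who stop treatment to keep attending visits. For those who withdraw, it asks for the end-of-study evaluations where possible.
- Protocol 9.3.1.2 calls the MADRS clinician-rated and names no rater.
- Protocol 9.3.1.4: "The CGI-S will be administered by the Investigator or a Sub-Investigator". Protocol 9.3.1.5 has the same arrangement for CGI-I.
- Protocol 9.3.3.3.3.1: "The C-SSRS will be administered by the Investigator".
- Protocol 10.2.2.5 has the Investigator judge the causality of adverse events.
- SAP 4.1 and 9.1 make the MADRS the primary efficacy measure. SAP 5.3 defines the mITT set without reference to unblinding, and SAP 5.4 leaves the major-violation criteria to be set before database lock.

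**The concern.** Some loss of blinding cannot be avoided when an Investigator breaks a code to manage an emergency. The notification sentence goes further: it makes it mandatory to pass the code to a group that the section does not define. A site that follows it literally loses the simplest remedy, which is to have a colleague who does not know the treatment do the later ratings.

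The primary measure is clinician-rated, and so are both CGI scales. A rater who knows the treatment may score differently, so the risk falls on the outcomes the SAP sets out to compare. Causality judgements are exposed in the same way. Because the SAP has no rule for ratings made after unblinding, they would enter the main analysis unmarked, and nobody would have decided in advance whether they should count.

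**Working it through.** **Step 1: compare the sentences in Protocol 8.6.**

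- The opening rule and the notification sentence both use the term study personnel. The first says they are blinded, apart from two named functions. The second says they are told the code for an unblinded subject. Nothing marks the second as a limited exception, and its only restriction protects the other subjects. The two conflict.
- The instruction to withhold the code has a narrow scope. It covers the Investigator's notice to the medical monitor after an emergency unblinding that was not discussed in advance. Whether it also conflicts with the notification sentence depends on an undefined term:
  - If study personnel includes the medical monitor, the conflict is direct.
  - If it means site staff only, the code is kept from the monitor but given to the people who may rate the subject.

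The conflict with the opening rule exists on both readings.

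**Step 2: can the subject still be rated by someone who was told?** Protocol 8.6 does not mention ratings, so this is an inference. Three things support it:

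- Withdrawal is optional (8.6).
- Visits are encouraged to continue after treatment stops (7.3).
- Even on withdrawal, the Early Termination visit includes MADRS, CGI-S, CGI-I and C-SSRS (9.1.5).

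No section requires a blinded replacement rater. SAP 9.1.1 and 9.1.3 fill missing values by LOCF, so if an early-termination rating made after unblinding is the last observation, it can supply all later weeks.

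**Step 3: size.** The plan states no figure for this, so there is none to reproduce.

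- n = 30 per arm (Protocol 12.2; SAP 9.5)
- W = 5 post-baseline weeks: 1, 2, 3, 4 and 6 (SAP 9.1.2). The primary test is the overall treatment effect, taken here as the equally weighted mean of the five weeks.
- b = 6 MADRS points of rater bias. This is an assumption; no document supplies it.
- k = 1 affected subject in the arm. This is also an assumption.
- v = number of that subject's weekly values affected

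Shift in the arm's overall mean = k × b × v / (n × W) = 6v / 150

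| Weeks affected | v | Shift (points) |
|---|---|---|
| Week 6 only | 1 | 6/150 = 0.04 |
| Weeks 4 and 6 | 2 | 12/150 = 0.08 |
| Weeks 2, 3, 4 and 6 | 4 | 24/150 = 0.16 |
| All five | 5 | 30/150 = 0.20 |

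The shift is proportional to b and to k:

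- Halving b to 3 gives 3/150 = 0.02 to 15/150 = 0.10.
- Doubling b to 12 gives 12/150 = 0.08 to 60/150 = 0.40.
- Two affected subjects at b = 6 also give 0.08 to 0.40.

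**The case against.** The strongest reply is that this is one loose sentence with a rare and small effect. Protocol 8.6 discourages unblinding that would not alter how an emergency is handled, and requires prior discussion with the medical monitor in every non-emergency case. Protocol 10.2.4 adds that unblinding is usually unnecessary even after a serious event. There may be no unblindings at all. Safety has no formal comparison (Protocol 12.4.3), so biased causality judgements would touch descriptive tables only. The Per Protocol criteria are still open and could exclude such subjects. All of this stands, and it limits the size of the problem. It does not remove the conflict in an operative instruction, and an open criterion is not a rule.

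A reader might also infer four stronger things that the documents do not support:

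- *That 8.6 flatly forbids what it then orders.* The instruction not to reveal the code covers only the notice to the medical monitor. It collides with the notification sentence only if study personnel includes the monitor.
- *That the code necessarily reaches sponsor staff.* The notification sentence does not name them, and the separate sentence keeping sponsor management and monitoring staff blinded is not lifted.
- *That the person who opens the envelope must rate the primary endpoint.* No MADRS rater is named, and a Sub-Investigator may rate CGI-S and CGI-I. Only the C-SSRS is reserved to the Investigator. Biased ratings are a risk, not a certainty.
- *That one known code reveals its neighbours in the permuted-block schedule.* Block size is not stated, numbers run in sequence, and centre is not a blocking factor (Protocol 8.5). Adjacent numbers may belong to other sites.

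**Conclusion.** The point holds as a conflict in Protocol 8.6 between the rule that study personnel are blinded and the unrestricted order to tell them an unblinded subject's treatment, together with a gap in the SAP on ratings made afterwards. That later ratings would be made by informed staff is a well-supported inference rather than a stated procedure.

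The numerical effect is small. With one affected subject among 30 and an assumed 6-point bias, the arm's overall MADRS mean shifts by 0.04 to 0.2 points. The upper end requires all five weekly values to be affected. The figures rest on an assumed bias, equal weighting of weeks and an unknown number of unblindings.

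The change should still be made: the exposure is avoidable, the instruction cannot be followed consistently as it stands, and the repair costs very little.

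**What to change.** **Protocol 8.6.** Replace the notification sentence with wording to this effect: *The assignment is disclosed only to those who need it to manage the emergency or to meet safety-reporting obligations. All other site, sponsor and data-management personnel, including the medical monitor, remain blinded.* Keep the two functions already excepted in the opening rule.

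**Later ratings.** Add that where an already qualified Investigator or Sub-Investigator at the site is still blinded, that person does the subject's later MADRS and CGI ratings. This cannot cover everything: an Investigator who opened the envelope knows the code, and the protocol reserves the C-SSRS to the Investigator. Those ratings can only be flagged.

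**SAP.** Flag efficacy and causality ratings made after unblinding. This needs the date of each unblinding to be on record; Protocol 10.2.6.1 asks for it only in serious adverse event reports. Add a sensitivity analysis of the primary endpoint that sets post-unblinding MADRS ratings to missing, and state how those values are handled. Under LOCF, say what happens when no post-baseline rating precedes the unblinding. Also correct SAP 4.4, which cites Protocol 8.7 for unblinding; the text is in 8.6.

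**To reconcile.** The emergency paragraph of 8.6 asks for the date and reason of study drug discontinuation, while the next paragraph leaves withdrawal open. The sponsor should make clear how the two fit together.

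**Cost.** Wording in two documents, a recorded unblinding date, and a few ratings left out of one sensitivity analysis. The main analysis and emergency access to the code are unchanged. The replacement rater applies only where a qualified blinded person is already on site, so no new staff are required.

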8.7 Selection of Doses in the Study

The dose of AXS-05 (105 mg bupropion, 45 mg DM), titrated to twice daily, was selected based on the results of three completed Axsome-sponsored, pharmacokinetic Phase 1 trials of the combination of bupropion and DM. The selected dose combination resulted in an increase in DM plasma concentrations into a potentially therapeutic range.

The dose of bupropion SR is 105 mg, titrated to twice-daily administration. This dose was selected because it is equal to the dose of bupropion in AXS-05.

8.8 Selection of Timing of Dose

A significant food effect has not been reported for the individual components of AXS-05. AXS-05 and bupropion SR tablets are dosed on an empty stomach (at least 2 hours pre- or 2 hours post-prandial) in this trial to match the dosing in the completed Phase 1 trials of AXS-05.

8.9 Dose Adjustment Criteria

Dose adjustment is not recommended in this study. If a subject misses a dose, or if a dose is skipped due to AEs, if possible the subject should continue in the study and take study drug at the designated times.

8.10 Drug Accountability

The Investigator must maintain adequate records showing the receipt, dosing, or other disposition of the study drug provided, including the date, quantity, batch or code number, and identification of subjects (subject number and initials) who received it. An inventory of study drug should be performed by authorized personnel upon receipt to confirm contents match the packing slip and that the all product packaging is received and in good condition. If product received does not correspond to the packing slip or is damaged, the Axsome study team should be contacted immediately and the inventory quarantined until further instructions are provided.

The Investigator will not supply the study drug to any person except those named as Sub-Investigators on the Form FDA 1572, designated study personnel, and subjects in this study. The Investigator will not dispense the study drug from any study sites other than those listed on the Form FDA 1572. The study drug may not be relabeled or reassigned for use by other subjects. If any of the study drug is not dispensed; is lost, stolen, spilled, unusable; or is received in a damaged container, this information must be documented and reported to Axsome and appropriate regulatory agencies, as required.

Upon completion of the study, the study drug (partly used, unused, and empty packaging) must be left in the original packaging and returned to Axsome or its designee for destruction.

8.11 Treatment Compliance

Study drug compliance will be closely monitored by counting the number of tablets dispensed and returned ______.

Subjects will be instructed to bring any unused study drug and empty containers to the clinic on Days 7, 14, 21, 28 and 42 (Visits 4-8), or at the time of early study discontinuation. Before new study drug is dispensed at each visit, every effort will be made to collect the unused study drug to confirm compliance. Investigators will perform drug accountability of study drug at each visit to determine a subject's usage. Study drug compliance will be assessed at the 80% level.

If non-compliance is determined, the site will be notified in writing and noncompliant subjects may be discontinued from the study. Discontinued subjects should return for an Early Termination visit, performing all the study assessments for Visit 8/ET and then complete the follow-up visit one week after the final dose of study drug (Visit 9).

8.12 Prior and Concomitant Therapies

Medication history during the previous 1 year (5 years in the case of psychiatric drug history) will be recorded at Screening (Visit 1) in the CRF. Thereafter, any changes in concomitant medications or new medications added will be recorded in the CRF.

At each visit, subjects will be queried as to whether or not they have taken any concomitant medications and, if so, the Investigator will record the medications taken and the reasons for their use. All concomitant medications and treatments used (including over-the-counter medications and herbal supplements) will be recorded in the source document and on the appropriate CRF.

8.12.1 Prohibited Therapies

The investigator should consult with the Axsome Medical Monitor if he/she is unsure whether a certain medication is prohibited.

Psychotherapy for depression may not be initiated, terminated, or changed during the course of the study (Support meetings or counseling [e.g., marital counseling] are allowed provided they are no more frequent than weekly and do not have treatment of depression as their objective).

Phototherapy is prohibited during the course of the study and may not have been initiated or terminated within 1 month of Visit 1.

Subjects who receive excluded therapies will be ineligible for continuation in the study at the discretion of the Sponsor and medical monitor.

8.13 Treatment after the End of Study

After the end of the study, each subject will be treated according to standard clinical practice.

9. STUDY PROCEDURES

Subjects will provide written informed consent before any study-related procedures are initiated, including the cessation of prohibited concomitant therapy.

For the timing of assessments and procedures throughout the study, refer to the Schedule of Assessments (Section 17.2). Throughout the study, every reasonable effort should be made by study personnel to follow the timing of assessments and procedures in the schedule of assessments for each subject. If a subject misses a study visit for any reason, the visit should be rescheduled as soon as possible.

9.1 Study Periods, Visits, and Procedures

9.1.1 Visit 1, Screening (Days –28 to –1)

Subjects will be screened within 28 days before randomization in the study. The following procedures will be performed at Screening:

- Provide the subject with the informed consent document and explain the rationale for the study, providing ample time for participants and authorized representatives to ask questions. Consent will be obtained before any subsequent screening related procedures are performed.
- Review inclusion/exclusion criteria.
- Review and record: Patient medical/psychiatric history and demographics.
- Review and record: Medications currently being taken or taken within the previous 1 year (5 years in the case of psychiatric drug history) of Screening (including OTC medications, vitamins, and supplements). Determine medication washout requirements and duration. Subjects who are receiving prohibited medications (e.g., antipsychotics, antidepressants, anticonvulsants/mood stabilizers, anxiolytics, and sedatives/hypnotics) except as specifically allowed, will require a washout period. All prohibited medications should be washed out before Visit 2.
- Perform a complete physical examination (excluding breast and genitourinary examination) with review of body systems.
- Record vital signs: Blood pressure, pulse, respiratory rate, and oral temperature after subject has been seated for 5 minutes.
- Measure height and weight.
- Collect blood and urine samples for central clinical laboratory tests (hematology, serum chemistry, urinalysis, thyroid panel, and serum ethanol); see Section 9.3.3.2.1 for a complete list of required laboratory tests.
- Collect urine for an on-site urine drug screen and urine pregnancy test (if female).
- Conduct SCID-5-CT interview to confirm MDD diagnosis.
- Administer evaluations:
 - MADRS (≥ 25 inclusive)
 - CGI-S (\geq 4 inclusive)
 - o QIDS-SR-16
 - Columbia Suicide Severity Rating Scale (C-SSRS) (lifetime)

•

